3.3.3.2.4 Neuroglycopenic, Autonomic and Total Symptom scores

The average Neuroglycopenic, Autonomic and Total Symptom scores (ANS, AAS, and ATS) will be summarized descriptively at each of the protocol defined time points (section 3.2.1) for each treatment group.

Additionally, this will also be presented graphically.

This will be done for ITT population, and will be done with time based on both “receiving glucagon” and “decision to dose”.

3.3.3.2.5 Symptom relief of hypoglycemia

The time to symptom relief will be presented descriptively.

A survival analysis will be done to comparing the difference between treatment groups. P-value for the difference will be reported.

This will be done for ITT population only, and will be done with time based on both “receiving glucagon” and “decision to dose”.

3.3.3.2.6 The time to the minimal score post baseline

The time to the minimal score will be summarized descriptively for each treatment.

A survival analysis will be done to comparing the difference between treatment groups. P-value for the difference will be reported.

This will be done for ITT population only, and will be done with time based on both “receiving glucagon” and “decision to dose”.

3.3.3.2.7 The time to first reporting of “no” for the global hypoglycemia question

The time to first reporting of “no” for the global hypoglycemia question will be summarized descriptively for each treatment. In rare cases if a subject does not answer “no,” the total time of 180 minutes will be used in the summary, but noted in the footnote.

A survival analysis will be done to compare the difference between treatment groups. P-value for the difference will be reported. Again, if a subject does not answer “no,” the total time of 180 minutes will be used, but noted as a censored value in the analysis model.

This will be done for ITT population only, and will be done with time based on both “receiving glucagon” and “decision to dose”.

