2 INVESTIGATIONAL PLAN

2.1 STUDY DESIGN AND RANDOMIZATION

2.1.1 Study Design

This is a non-inferiority, multi-centered, randomized, controlled, single-blind, two-way crossover efficacy and safety in-patient study in subjects with Type 1 diabetes mellitus (T1D).

Table 2-1: Randomized treatment sequence

Group	Dose 1	Dose 2
1	G-Pen™ 1 mg	Lilly 1 mg
2	Lilly 1 mg	G-Pen™ 1 mg

The procedure consists of:

1. Inducing hypoglycemia by IV administration of regular insulin diluted in normal saline until the subjects reach a verified stable hypoglycemic state.
2. Treating subcutaneously with either 1 mg Lilly Glucagon or 1 mg G-Pen™ (glucagon injection).

Blood glucose levels will be monitored for up to 180 minutes post-dosing. Subjects will also complete a questionnaire about symptoms of hypoglycemia during the hypoglycemia induction phase and for up to 180 minutes after treatment with glucagon.

The specific hypoglycemia induction procedures and justification, and rules for interruption and termination of dosing are listed in the protocol.

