2.1.2 Sample Size

For the primary objective, a failure is recorded if the subject's plasma glucose fails to rise above 70.0 mg/dL within 30 minutes of administration of the dose of glucagon. Using this criterion, a sample size of 85 randomized subjects yields probabilities of G-Pen acceptance of 88% if the population failure rate differences of G-Pen and control are within 2%, and the rate of missing observations is within 5%.

Subjects will be recruited at approximately 6 clinical sites with a goal of no single center accounting for > 20% of the total sample.

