3 STATISTICAL AND ANALYTICAL PROCEDURES

3.1 ANALYSIS POPULATIONS

3.1.1 Intent-to-Treat (ITT) population

The intent-to treat (ITT) population is defined as all subjects randomized. A subject's randomized treatment will be used for analysis regardless of the actual treatment received.

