3.2.5.2.6 The time to the minimal score post dose

This will be calculated for sub-scales ANS, AAS and ATS as the difference (in mins) between the actual time when the minimal number is observed and the time of receiving glucagon. Actual Time will be used to the calculation of the following variables.

- Subjects who never develop symptoms will be assumed to have a value of 0.

This parameter will be analyzed both on time from receiving glucagon and from a decision to dose.

3.2.5.2.7 The time to first reporting of “no” for the global hypoglycemia question will be defined as below:

This will be calculated as the difference (in mins) between the actual time when the first “no” for “Overall Assessment of Hypoglycemia” is observed and the time receiving glucagon. Actual Time will be used to the calculation of the following variables.

- Subjects who never develop symptoms (never answers No) will be assumed to have a value of 0.
- In very rare cases, if subject answers Yes all the way to the last time point, the total time will be recorded. (And it will be analyzed based survival model.)

This parameter will be analyzed both on time from receiving glucagon and from a decision to dose.

3.2.5.2.8 The Glucagon Preparation Time:

Glucagon preparation time (min) is defined as the time between “decision to dose” and time of study drug administration to the abdomen. Actual Time will be used to calculate this variable.

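### Time to first *no* on the global hypoglycemia question: the fixed 180-minute censoring ignores shorter observation and conflicts with the derivation section, which also carries a misworded 0-minute rule

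*SAP*

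**What the plan says.** Two sections of the SAP govern this variable.

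- **Derivation (3.2.5.2.7).** The time runs from receiving glucagon to the first *no*, and "Actual Time will be used to the calculation of the following variables". For the very rare subject who never reports relief, "if subject answers Yes all the way to the last time point, the total time will be recorded", to be handled in a survival model. A separate bullet gives a value of 0 to subjects who never develop symptoms, and its parenthesis describes them as subjects who never give the answer No. Two clocks are required: "This parameter will be analyzed both on time from receiving glucagon and from a decision to dose".
- **Analysis (3.3.3.2.7).** For a subject without a *no*, in the descriptive table "the total time of 180 minutes will be used in the summary, but noted in the footnote". In the survival analysis, "the total time of 180 minutes will be used, but noted as a censored value in the analysis model". The analysis is in the ITT population only.

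Two other places bear on it. Section 2.1.1 has the symptom questionnaire completed "for up to 180 minutes after treatment with glucagon". Section 3.1.1 sets no condition on completed observation: "The intent-to treat (ITT) population is defined as all subjects randomized".

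**The concern.** A censoring time should be the last moment at which the subject was known not to have had the event. The rule in 3.3.3.2.7 replaces that moment with a constant. A subject whose last answer is *yes* at 30 minutes then stays in the risk set as unrelieved until 180 minutes, and the descriptive mean takes 180 as if it had been observed. The derivation section points to a different time for that subject. Its 0 rule, read literally, points to a third value at the opposite end of the scale.

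At stake is whether two programmers working from this SAP would build the same dataset, and whether subjects with unknown outcomes are analysed as known to be unrelieved.

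**Working it through.** The plan states no figure for this rule, so there is nothing to reproduce. The check compares the rules and then sizes the difference under stated assumptions.

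**Step 1. The rules side by side, receiving-glucagon clock.**

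| Subject with no *no* | Total-time rule, 3.2.5.2.7 | 3.3.3.2.7 | Literal 0 rule, 3.2.5.2.7 |
|---|---|---|---|
| Answers *yes* through 180 min | 180 (apart from actual-time deviations) | 180, censored | 0 |
| Last answer *yes* at 30 min | 30 | 180, censored | 0 |

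In the first row the total-time and 180-minute rules agree. In the second row they differ by 180 − 30 = 150 minutes of unobserved time at risk. The 0 rule conflicts with both in either row. Its lead phrase (no symptoms) and its parenthesis (no *no*) describe opposite subjects, so the parenthesis is probably a slip for never answering *yes*.

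**Step 2. Decision-to-dose clock.** Full follow-up after injection lasts 180 minutes plus the preparation time, so a constant 180 does not equal the total time even for a complete subject. This changes the risk set only if another subject first answers *no* after minute 180 on that clock.

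**Step 3. The largest effect four leavers can have.** The number of subjects is from 2.1.2 ("a sample size of 85 randomized subjects"). The number of leavers, 4, is an assumption. It borrows the 5% missing rate that 2.1.2 allows for the primary outcome (0.05 × 85 = 4.25). Assume 30, 30, 15 and 6 subjects first answer *no* at 10, 20, 40 and 60 minutes (81 in all), and 4 leave at 25 minutes without a *no*. The Kaplan-Meier proportion still hypoglycemic at 60 minutes is:

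- censored at 25: (55/85) × (25/55) × (6/21) × (0/6) = 0, so relief is 100%;
- censored at 180: (55/85) × (25/55) × (10/25) × (4/10) = 4/85 = 0.047, so relief is 81/85 = 95.3%.

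The difference is 4.7 percentage points. This is a ceiling, because each leaver carries a weight of 1/85 and all four weights have moved. The Kaplan-Meier quartiles are 10, 20 and 40 minutes under both rules.

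**Step 4. Less extreme patterns.** Event times are exponential quantiles with an assumed median of 15 or 30 minutes, rounded up to 5 minutes and capped at 175, with 85 subjects. Each cell gives censoring at the last answer, then at 180.

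| Median | Leavers, last seen | Still hypoglycemic at 60 min | Difference (points) | Arithmetic mean (min) |
|---|---|---|---|---|
| 15 | 4 at 0 | 0.062, 0.106 | 4.4 | 23.0, 31.5 |
| 15 | 4 at 30 | 0.071, 0.106 | 3.5 | 24.4, 31.5 |
| 15 | 4 at 60 | 0.106, 0.106 | 0 | 25.8, 31.5 |
| 30 | 4 at 0 | 0.247, 0.282 | 3.5 | 42.9, 51.4 |
| 30 | 4 at 30 | 0.259, 0.282 | 2.3 | 44.3, 51.4 |
| 30 | 4 at 60 | 0.282, 0.282 | 0 | 45.7, 51.4 |
| 15 | 1 at 30 | 0.062, 0.071 | 0.9 | 24.2, 25.9 |
| 30 | 1 at 30 | 0.253, 0.259 | 0.6 | 44.8, 46.6 |

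The shift in the mean follows directly: 4 × (180 − 30)/85 = 7.1 minutes for four leavers at 30 minutes, and 150/85 = 1.8 minutes for one. Neither mean is a sound summary, since both average censored times as observed.

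**The case against.** The strongest reply is that the two sections describe one case. The last protocol time in 3.2.2 is 180 minutes, and 3.3.3.2.7 calls 180 minutes the total time, which is the derivation section's own term. On that reading both mean a subject seen to the end and still answering *yes*, and early leavers are simply not addressed. This stands for the fully observed subject. It does not rescue the rule for others: 3.3.3.2.7 applies to any subject without a *no*, in a population of all randomized subjects, and the default in 4.1 against imputation gives way where a section specifies a value.

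It is also fair that this is an in-patient study, that the SAP calls these cases rare, and that nothing in it says subjects leave early while still hypoglycemic. The leaver counts above are therefore assumptions, and the 4.7 points is a constructed maximum.

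Keeping an early leaver as unrelieved is a recognisable conservative choice, and censoring at the last answer has an assumption of its own: that leaving is unrelated to the chance of relief. That stands, and the fix allows for it.

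A reader might infer that the p-value for the symptom-relief objective depends on this rule. It does not do so as a whole: symptom relief is defined on the three mean scores in 3.2.5.2.5 and has its own survival analysis in 3.3.3.2.5. A reader might also infer that the decision-to-dose clock penalises the drug that takes longer to prepare. The discrepancy is real, but by Step 2 its consequence is close to nil.

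**Conclusion.** The point holds as a limited defect in one secondary ITT endpoint. A stated rule assigns unobserved time at risk to anyone observed for less than 180 minutes without a *no*. It departs from the actual-time derivation for those subjects, and it enters 180 in the descriptive summary as an observed value, disclosed only by footnote. The literal 0 rule is the sharper conflict, 0 against 180 censored for the same subject.

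The effect is probably small. With 4 assumed leavers of 85 it is at most 4.7 points in Kaplan-Meier relief, about 2 to 4 points at 60 minutes when they are last seen by 30 minutes, and about 7 minutes in the mean. With one leaver at 30 minutes it is under 1 point and under 2 minutes. A reader might go further and conclude that the rule makes one drug look slower. That would need early leaving to differ between treatments, which the SAP does not suggest, and no treatment comparison was calculated here. The primary non-inferiority analysis is unaffected.

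**What to change.** - **3.3.3.2.7:** replace the fixed 180 minutes in the survival analysis with censoring at the actual time of the subject's last completed answer to the global question, measured from the time origin in use (receiving glucagon or decision to dose). State how a period with no post-dose answer is handled.
- **3.2.5.2.7:** use the same censoring wording, and limit the value of 0 to subjects who never answer *yes*, removing the description of them as never answering No.
- **Descriptive summary:** give the Kaplan-Meier median and quartiles by treatment, so that censored times are not averaged as observed.
- **Sensitivity analysis:** repeat with the 180-minute rule, because the main analysis would now assume non-informative early leaving.

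The cost is SAP wording and one additional run. The variable is already derived from actual times, so no new data are needed.

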3.3.3.2.8 The Glucagon Preparation Time

The glucagon preparation time will be summarized descriptively for each treatment.

A mixed model with treatment, period and sequence as fixed factors and subject as a repeated factor will be applied to compare the least square mean differences. Log transformation will be applied if skewness is observed. Unstructured structure will be used for the covariance matrix unless model failed. In such case, structured covariance matrix will be selected based on the one given the smallest AIC (Akaike Information).

This will be done for both the ITT and PP populations.

3.3.4 Safety Analysis

All safety analyses will be performed using the safety population. Note, actual received treatment will be used. Analyses will be based on time of receiving glucagon if protocol time is involved.

3.3.4.1 Adverse Events (AE)

All AEs will be coded using the latest Medical Dictionary for Regulatory Activities and summarized descriptively by system organ class and study drug. A summary table indicating the number and the percentage of exposed subjects having at least one AE will be made. A similar table will provide a breakdown of AEs (all and related) by intensity level (mild, moderate, severe).

Note that subgroup analysis is needed for this (section 3.3.5.1)

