1.2.2 Secondary Objectives

The secondary objectives of this study are:

- To demonstrate the efficacy (either return to plasma glucose >70.0 mg/dL or an increase in plasma glucose ≥ 20 mg/dL within 30 minutes post study drug injection) of G-Pen 1 mg (test) to be non-inferior to Lilly Glucagon 1 mg (reference), in T1D subjects in a state of insulin-induced hypoglycemia.
- To demonstrate the efficacy (return to plasma glucose >70.0 mg/dL or alleviation of all neuroglycopenic symptoms at 30 minutes post study drug injection) of G-Pen 1 mg (test) to be non-inferior to Lilly Glucagon 1 mg (reference), in T1D subjects in a state of insulin-induced hypoglycemia.
- To compare the pharmacodynamics characteristics of G-Pen 1 mg (test) versus Lilly Glucagon 1 mg (reference) in T1D subjects who are in a state of insulin-induced hypoglycemia.
- To compare G-Pen (test) and Lilly Glucagon (reference) with regards to hypoglycemia symptom relief.
- To compare G-Pen (test) and Lilly Glucagon (reference) with regards to the preparation time required to inject to the abdomen from a decision to treat.
- To compare the safety and tolerability of G-Pen 1 mg (test) versus Lilly Glucagon 1 mg (reference) in T1D subjects who are in a state of insulin-induced hypoglycemia.

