3.3 STATISTICAL METHODS

3.3.1 General guideline for descriptive summaries

For continuous variables, mean, standard deviation, minimum, and maximum will be presented for each treatment group.

For categorical variables, count and % of subjects/counts in each treatment group will be presented.

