3.3.5 Other statistical Analysis

3.3.5.1 Subgroup Analysis

The following safety and efficacy variables will be summarized descriptively by gender (male, female), age (18.0 – 64.9 years, 65.0 years and above), and race (non-Hispanic Whites, Hispanics, and African-Americans):

- AE (Any)
- Time (min) to glucose >70 mg/dL within 30 minutes of receiving glucagon

This will be done in the ITT population only, and will be done with time based on both “receiving glucagon” and “decision to dose”.

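### Adverse events are tabulated per drug only, so the AE part of the safety comparison has no within-subject contrast or interval despite the crossover design

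*SAP*

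**What the plan says.** Section 1.2.2 lists as a secondary objective: "To compare the safety and tolerability of G-Pen 1 mg (test) versus Lilly Glucagon 1 mg (reference) in T1D subjects". No safety hypothesis or margin is attached. Section 2.1.1 describes a "single-blind, two-way crossover efficacy and safety in-patient study", so each subject is planned to receive both drugs.

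For adverse events, section 3.3.4.1 Adverse Events (AE) says that they are "summarized descriptively by system organ class and study drug". It then specifies two tables. The first is incidence: "A summary table indicating the number and the percentage of exposed subjects having at least one AE will be made". The second is intensity: "A similar table will provide a breakdown of AEs (all and related) by intensity level (mild, moderate, severe"). The general rule in 3.3.1 is the same: "For categorical variables, count and % of subjects/counts in each treatment group will be presented". The AE subgroup analysis in 3.3.5.1 is descriptive as well: "The following safety and efficacy variables will be summarized descriptively by gender (male, female), age (18.0 – 64.9 years, 65.0 years and above").

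Elsewhere the SAP uses the within-subject structure:
- the primary endpoint is a per-subject difference in failure score (3.2.5.1);
- the pharmacodynamic parameters (3.3.3.2.3) and preparation time (3.3.3.2.8) get a mixed model with treatment, period and sequence, and subject as a repeated factor;
- among the safety variables, VAS discomfort gets a mixed model comparing treatments if enough scores exceed zero (3.3.4.3.1).

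**The concern.** The objective is comparative and the design makes each subject his or her own control, but the AE analysis stops at two columns of counts and percentages. A reader who wants to judge the difference has only the two marginal rates, and can attach uncertainty to it only by treating the columns as independent groups.

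The counts that carry the crossover comparison are the subjects with an AE on G-Pen only and those with one on Lilly Glucagon only. The two marginal percentages do not determine them. If AE-proneness is a trait of the subject, so that the two outcomes are positively correlated, the independent reading overstates the uncertainty. The report then says less about the AE difference than the data allow. If no contrast is written in beforehand, any contrast produced later is a post hoc choice.

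**Working it through.** **Figures in the plan.** The AE section states no rate, difference or precision, so there is no AE figure to reproduce. The 88% in 2.1.2 concerns non-inferiority on the primary endpoint and does not enter here.

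**Inputs.** N = 85 is the randomized number in 2.1.2, taken here as the number exposed to both drugs, which is the best case. The AE counts (25 on G-Pen, 16 on Lilly Glucagon) and the within-subject correlation φ are assumptions, since the SAP gives neither.

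**Step 1: margins.** p1 = 25/85 = 0.294 and p2 = 16/85 = 0.188, so d = 9/85 = 0.106. The variance terms are p1(1−p1) = 0.2076 and p2(1−p2) = 0.1528, which sum to 0.3604. Also √(0.2076 × 0.1528) = 0.1781.

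**Step 2: read as two independent groups.** SE = √(0.3604/85) = 0.0651 and 1.96 × SE = 0.128. The interval is −2.2 to 23.4 points.

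**Step 3: paired.** SE = √[(0.3604 − 2φ × 0.1781)/85]. This equals √[(p10 + p01 − d²)/85], where p10 and p01 are the discordant proportions.

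| φ | Variance term | Half-width (points) | 95% CI (points) | Narrower than Step 2 |
|---|---|---|---|---|
| 0 | 0.3604 | 12.8 | −2.2 to 23.4 | 0% |
| 0.3 | 0.2535 | 10.7 | −0.1 to 21.3 | 16% |
| 0.5 | 0.1823 | 9.1 | 1.5 to 19.7 | 29% |
| 0.7 | 0.1111 | 7.1 | 3.5 to 17.7 | 44% |

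**Step 4: the same planned table from different data.** Two whole-number splits share the margins 25 and 16.
- 14 on G-Pen only, 5 on Lilly only, 11 on both, 55 on neither (φ about 0.42): SE = √[(19/85 − 0.0112)/85] = 0.0500, interval 0.8 to 20.4 points.
- 20 on G-Pen only, 11 on Lilly only, 5 on both, 49 on neither (φ about 0.02): SE = √[(31/85 − 0.0112)/85] = 0.0645, interval −2.1 to 23.2 points.

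The planned table would print 25 (29.4%) and 16 (18.8%) in both cases. One paired interval excludes zero and the other does not.

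These are simple Wald intervals, used only to show the size of the effect.

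**The case against.** The strongest reply is that nothing here is an error. Descriptive AE tables by drug are conventional in a trial sized for efficacy. The SAP states no safety hypothesis or margin, 3.3.4.1 agrees with the general rule in 3.3.1, and side-by-side percentages are a comparison of a kind. This stands: the planned table is correct as far as it goes, and the point is an improvement to it. What remains is that the comparison as planned makes no use of the pairing that the design provides.

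A reader might infer more than the document supports, in five ways.

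- *That the whole safety and tolerability objective lacks a contrast.* It does not: 3.3.4.3.1 plans a conditional treatment comparison for VAS discomfort. That model concerns injection-site discomfort and leaves AE incidence untouched.
- *That every subject will have both exposures.* That is the design intention. The safety population is all randomized subjects by actual treatment (3.1.3), AE percentages are of exposed subjects, and 3.2.5.1 provides for missing treatment outcomes. Some subjects may contribute to one column only.
- *That the margins could hide anything from a clear excess to a very wide interval.* Zero overlap (25 on G-Pen only, 16 on Lilly only) would give −4.0 to 25.2 points, but it needs a within-subject correlation of about −0.31. The illustration does not rely on it.
- *That the precision gain is assured.* It depends on a positive correlation, about which the SAP says nothing. At zero there is no gain.
- *That the discordant counts will be unavailable.* Subject-level data will hold them, and the planned table list in Appendix 1 is not shown and might include listings. What can be said is that the text of 3.3.4.1 describes no paired table or contrast.

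**Conclusion.** The point holds for adverse events only and is of low severity. The AE part of a comparative objective in a crossover trial is planned as separate counts and percentages per drug, with no within-subject contrast and no interval.

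Under the assumed 25 versus 16 events in 85 subjects, pairing would narrow the 95% interval by about 16% to 44% for correlations of 0.3 to 0.7, and not at all at correlation 0. The rates and correlations are assumptions. What does not depend on them is that the planned table cannot show which of these cases applies.

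The document does not support a claim that the safety objective as a whole goes unanalysed, or that the planned AE percentages are wrong. No sample size, power or significance level is affected.

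**What to change.** In 3.3.4.1 Adverse Events (AE), keep the planned tables and add, for any AE and for any related AE, among subjects exposed to both drugs:

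1. the within-subject cross-tabulation: G-Pen only, Lilly Glucagon only, both, neither;
2. the paired risk difference (G-Pen minus Lilly Glucagon) with a 95% confidence interval by a paired method such as Tango or Newcombe.

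Label both as estimation and attach no p-values. Do not require them for each system organ class: with 85 subjects many classes would have very few discordant pairs, and the intervals would be uninformative and invite multiplicity questions.

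The cost is one extra table and about two sentences of SAP text, from data already collected. The downside is that subjects exposed to one drug only appear in the marginal table but not in the paired contrast, so the two denominators can differ and should be footnoted. If the sponsor prefers no contrast, the consistent alternative is to word the AE part of the objective in 1.2.2 as descriptive.
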